9.2 Background Characteristics

9.2.1 Subject Disposition

The number of subjects in the following categories will be summarized overall and by treatment group based on the All Subjects Set:

- All Subjects Set
- Randomized
- Randomized but not dosed
- Full Analysis Set
- Safety Set

The number and percentage of subjects in each of the following disposition categories will be summarized overall and by treatment group:

- Completed study drug treatment
- Prematurely discontinued the treatment and the reason for discontinuation
- Completed study
- Prematurely discontinued the study and the reason for discontinuation
- Enrolled in a rollover extension study

A listing will be provided for subjects who discontinued treatment or who discontinued study, with reasons for discontinuation.

9.2.2 Demographics and Baseline Characteristics

Demographics and baseline characteristics will be summarized overall and by treatment group, based on the FAS.

Demographic data will include the following:

- Age at screening (years)
- Sex (female and male)
- Ethnicity (Hispanic or Latino, not Hispanic or Latino, and not collected per local regulations)
- Race (White, Black or African American, Asian, American Indian or Alaska Native, Native Hawaiian or Other Pacific Islander, not collected per local regulations, and Other)

- Geographic region (Europe and Australia)

Baseline characteristics will include the following:

- Mutation (F/F, F/RF)
- Weight group (<40 kg, >=40 kg)
- BMI (kg/m²)
- BMI z-score
- Weight (kg)
- Weight z-score
- Height (cm)
- Height z-score

Disease characteristics will include the following:

- Baseline LCI_{2,5}
- Baseline ppFEV₁
- Baseline FEV₁
- Baseline score of CFQ-R respiratory domain
- Baseline sweat chloride

In addition, the following data listings will also be provided:

- Informed consent
- Subjects with any inclusion and exclusion criteria violation

9.2.3 Medical History

Medical history will be coded by using the Medical Dictionary for Regulatory Activities (MedDRA).

Based on the FAS, medical history will be summarized descriptively by system organ class (SOC) and preferred term (PT). The corresponding data listing will also be provided.

9.2.4 Prior and Concomitant Medications

Medications used in this study will be coded by using the World Health Organization Drug Dictionary (WHODD) and categorized as follows:

- **Prior medication:** any medication that started before the first dose date of study drug, regardless of when the medication ended.
- **Concomitant medication:** medication continued or newly received on or after the first dose date of study drug through the end of the TE period.
- **Post-treatment medication:** medication continued or newly received after the TE period.

A given medication may be classified as follows: prior, concomitant, post-treatment, both prior and concomitant, both concomitant and post-treatment, or prior, concomitant, and post-treatment.

If a medication has a completely missing or partially missing start date or stop date and it cannot be determined whether it was taken before the first dose date, concomitantly, or after the TE period, it will be classified as prior, concomitant, and post-treatment.

Prior medications and concomitant medications will be summarized descriptively by: 1) preferred name (PN); and 2) anatomic class (ATC) level 1, ATC level 2, and PN, on the FAS and presented by treatment group and overall. They will also be listed for each subject.

Details for imputing missing or partial start and/or stop dates of medication are described in [Appendix D](#).

9.2.5 Study Drug Exposure

Study drug exposure will be summarized based on the Safety Set, and presented by treatment group and overall.

Duration of study drug exposure (in days) will be calculated as: last dose date – first dose date + 1 day, regardless of study drug interruption.

Duration of study drug exposure will be summarized descriptively (n, mean, SD, median, minimum, and maximum). It will also be summarized in categories for exposure duration: >0 to ≤2 weeks, >2 to ≤4 weeks, >4 to ≤8 weeks, and >8 weeks, using counts and percentages. Additionally, the total study drug exposure, defined as the sum total of the study drug exposure across all subjects (in patient-weeks), will be provided.

9.2.6 Study Drug Compliance

Study drug compliance will be summarized based on the FAS, and presented by treatment group and overall.

Study drug compliance will be calculated as: $100 \times [1 - (\text{total number of days of any study drug interruption}) / (\text{duration of study drug exposure in days})]$.

Study drug compliance will be summarized descriptively (n, mean, SD, median, minimum, and maximum), and also in categories: <80% and ≥80% using frequency and percentage.

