#### 10.6 Compliance

To ensure treatment compliance, the investigator or designee will supervise all study drug dosing that occurs at the site. At each visit, site personnel will review that the subject is compliant with study drug dosing and remind the subject of study drug dosing requirements. Compliance will also be assessed by ongoing study drug count.

If a subject demonstrates continued noncompliance of study drug dosing despite educational efforts, the investigator will contact the medical monitor to discuss discontinuation of the subject from the study.

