#### **12.3.2.4 Study Drug Exposure and Compliance**

Duration of study drug exposure (in days) will be calculated as: last dose date – first dose date + 1 day, regardless of study drug interruption.

Exposure summaries will be based on the Safety Set.

Study drug compliance based on the number of tablets taken will be calculated as:  $100 \times [(total\ number\ of\ tablets\ dispensed) - (total\ number\ of\ tablets\ returned)] / (total\ number\ of\ tablets\ planned\ to\ be\ taken\ per\ day \times duration\ of\ study\ drug\ exposure\ in\ days)$ . The maximum percentage of tablets taken will be 100%.

Study drug compliance based on study drug exposure will be calculated as:  $100 \times [1 - (total\ number\ of\ days\ of\ any\ study\ drug\ interruption) / (duration\ of\ study\ drug\ exposure\ in\ days)]$ .

Study drug compliance will be summarized descriptively by n, mean, SD, SE, median, min, and max. They will also be summarized in categories: <80% and  $\geq 80\%$  using frequency tables.

Study drug compliance summaries will be based on the FAS.

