4 INTRODUCTION

This statistical analysis plan (SAP) Methods, which describes the planned analyses for Study VX16-661-115, is based on the most recent approved clinical study protocol (CSP), the most recent approved electronic case report form (eCRF), and the most recent approved eCRF completion guidelines.

Study VX16-661-115 is a Phase 3, double blind, parallel-group study to evaluate the efficacy and safety of tezacaftor (TEZ; VX 661) in combination with ivacaftor (IVA; VX 770) in subjects aged 6 through 11 years with cystic fibrosis (CF), homozygous or heterozygous for the *F508del-CFTR* mutation.

This SAP (Methods) documents the planned final statistical analyses of efficacy and safety endpoints defined in the VX16-661-115 study protocol. It also documents analyses for additional efficacy and safety variables not specified in the protocol.

[REDACTED]

The Vertex Biometrics Department or designee will perform the statistical analysis of the efficacy and safety data; SAS (Version 9.4 or higher) will be used to generate all statistical outputs (tables, figures, listings, and datasets). The SAP will be finalized and approved prior to the final clinical database lock and treatment unblinding for the study. If the methods in this SAP differ from the methods described in the protocol, the SAP will prevail.

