9.2.7 Important Protocol Deviations

Important protocol deviations (IPD) are a subset of protocol deviations that may significantly impact the completeness, accuracy, or reliability of the study data or that may significantly affect a subject's rights, safety, or well-being. IPD rules will be developed and finalized before database lock.

The protocol deviations that should be considered as potential IPDs include, but are not limited to:

- Subject entered the study despite violation of any inclusion or exclusion criteria
- Subject was less than 80% compliant with study drug for non-safety reason

- Subject received prohibited concomitant medications
- Subject received the wrong treatment or incorrect doses
- Subject remained in the study despite meeting withdrawal criteria

Occurrence of any of these events should be considered as potential IPDs, but a blinded team should categorize them as IPDs only if they have the potential to significantly affect the completeness, accuracy, or reliability of the study data or that may significantly affect a subject's rights, safety, or well-being.

IPDs (from the clinical database or from the site deviation log) will be summarized descriptively based on the FAS and presented by treatment group and overall. Additionally, IPDs will be provided in an individual subject data listing.

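### SAP 9.2.6 drops the protocol's tablet-count compliance and keeps a whole-day interruption formula, with interruption undefined, that cannot measure partial adherence to twice-daily dosing

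*SAP*

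**What the plan says.** **Protocol.** Section 12.3.2.4 sets out two measures. The first ("Study drug compliance based on the number of tablets taken will be calculated as") takes tablets dispensed minus tablets returned and divides by planned tablets per day times days of exposure, with a ceiling of 100%. The second ("Study drug compliance based on study drug exposure will be calculated as") is one minus the share of exposure days that were days of interruption. Compliance is to be summarised on the FAS, also split at 80%. Section 10.6 adds: "Compliance will also be assessed by ongoing study drug count". Table 3-1 schedules the drug count at Weeks 2, 4 and 8 and at the ETT Visit.

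**SAP.** Section 9.2.6 ("Study drug compliance will be calculated as") has a single formula, based on the "total number of days of any study drug interruption" divided by duration of exposure, with the same 80% split. The tablet count does not appear. Section 4 settles which document governs: "If the methods in this SAP differ from the methods described in the protocol, the SAP will prevail".

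**Deviations.** Section 9.2.7 of the SAP lists as a potential important protocol deviation (IPD): "Subject was less than 80% compliant with study drug for non-safety reason". The bullet does not say how compliance is measured. The same section states: "IPD rules will be developed and finalized before database lock".

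**The concern.** Each day has a morning and an evening dose, but the retained formula works in whole days. A subject who takes half of each day's tablets has no correct place on that scale: the day either counts as interrupted or it does not.

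The formula also depends on what is recorded as an interruption, and no definition is given. The documents use the word in different ways. Protocol Table 13-3 ties it to an adverse event, and Section 11.5.3 to liver-test results. The spirometry footnote to Table 3-1 uses it, with no such tie, for study drug not given on a visit day. Doses that are forgotten and skipped are covered separately in Section 9.7, where they are not called interruptions.

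At stake are the compliance table and the IPD summary. SAP 9.2.6 holds the only compliance measure in the SAP, so it is the natural input to the 80% bullet in 9.2.7. That bullet is aimed at non-safety reasons, whereas several uses of interruption in the documents concern safety events. Ordinary missed tablets are what the omitted measure was built to pick up. The efficacy analyses keep data whatever the adherence, so the compliance summary is where a reader would look to judge whether a weak LCI result reflects lack of effect or lack of dosing.

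**Working it through.** The plan states no expected compliance figure, so there is none to reproduce. The check applies the formulas to simple dosing patterns.

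**Inputs**
- Exposure: last dose date minus first dose date plus 1 (SAP 9.2.5). With the Week 8 Visit on target Day 57 (SAP Appendix A) and the last dose the evening before (Protocol 9.6), this is 56 − 1 + 1 = 56 days. Attendance exactly on the target day is an assumption.
- Planned tablets (Protocol Table 9-2): F/F 2 a day, 2 × 56 = 112; F/RF 3 a day (two morning, one evening), 3 × 56 = 168.

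**Formulas**
- Tablet count: 100 × (dispensed − returned) / planned, at most 100. All untaken tablets are assumed returned.
- Interruption: 100 × (1 − interruption days / 56).

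**Pattern 1: every evening tablet skipped**
- Tablet count, F/F: 56/112 = 50%.
- Tablet count, F/RF: 112/168 = 66.7%.
- Interruption, if skipped doses are not interruptions: 100 × (1 − 0/56) = 100%.
- Interruption, if any missed dose makes an interruption day: 100 × (1 − 56/56) = 0%.

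Neither reading gives the share of tablets taken. This result does not depend on the 56-day assumption.

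**Pattern 2: all doses missed on 12 scattered days**
- Tablet count, both genotypes: 44/56 = 78.6%, below 80%.
- Interruption, if the 12 days are recorded as such: 100 × (1 − 12/56) = 78.6%, the same.
- Interruption, if none is recorded: 100%.

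**Where each measure crosses 80%**

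| Measure | Last value at or above 80% | First value below 80% |
|---|---|---|
| Tablet count, F/F | 22 missed: 90/112 = 80.4% | 23 missed: 89/112 = 79.5% |
| Tablet count, F/RF | 33 missed: 135/168 = 80.4% | 34 missed: 134/168 = 79.8% |
| Interruption | 11 days: 45/56 = 80.4% | 12 days: 44/56 = 78.6% |

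**Range.** The Week 8 Visit may move by 5 days either way, so exposure can run from 51 to 61 days. The first number of wholly missed days that falls below 80% is then 11 at 51 days (40/51 = 78.4%) and 13 at 61 days (48/61 = 78.7%). The threshold shifts by one day; the contrast between the two measures does not.

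**The case against.** A reader might infer that subjects who miss many doses will be reported as 100% compliant, and that reported compliance is therefore biased upward. The documents do not establish this. The formula counts days of any interruption, and the Table 3-1 footnote uses the word for drug simply not given on a visit day. SAP 9.4.1.1 also recognises that the morning and evening agents can be interrupted separately. On a wide reading, the 12 missed days score 78.6%, exactly as by tablet count, and the subject who skips evenings scores 0%, an error in the opposite direction. Protocol 9.7 favours the narrow reading, but the position is ambiguity, not proven inflation.

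A reader might also infer that non-adherent subjects escape the 80% deviation rule. That goes too far as well. The bullet in SAP 9.2.7 cites no formula, the IPD rules are not final, the list is open, incorrect doses are a separate item, and the site deviation log is a further source. Tablet counts are still collected, and nothing prevents the blinded team from using them.

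The tablet count has its own upward bias: an unreturned tablet counts as taken. It should not replace the interruption measure, and the protocol did not rank one above the other.

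These objections remove the unconditional claims. They leave the omission itself, the missing definition, and the inability of a whole-day formula to score half-taken days.

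**Conclusion.** The point holds as a minor one. The governing document omits a protocol-specified measure without a reason in the visible text (parts of the SAP are redacted, so a reason may exist elsewhere). What remains cannot represent partial adherence: a subject who took 50% of tablets (66.7% for F/RF) scores 100% or 0% by convention alone. Scattered whole-day misses of about a fifth of the treatment period can be shown as 100%, but only if they are not recorded as interruption. The 80% bullet may miss ordinary non-adherence; whether it would depends on rules not yet written.

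The figures assume 56 days of exposure and complete return of untaken tablets. How often such patterns would occur cannot be derived from the documents.

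It would be wrong to infer any effect on the primary result. That analysis uses the FAS and includes measurements after treatment discontinuation, no model uses compliance, and SAP Section 8 defines no per-protocol set. The impact is confined to the descriptive compliance and IPD summaries.

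**What to change.** 1. In SAP 9.2.6, restore the tablet-count formula of Protocol 12.3.2.4 and summarise it beside the interruption measure, each with the 80% split.
2. Define interruption for the formula, stating whether a single skipped dose, or a whole day missed without an adverse event, counts.
3. In SAP 9.2.7, name the measures behind the 80% bullet and flag a potential IPD when either is below 80%, leaving the final classification to the blinded team as now planned.

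The cost is one formula and one extra table from data already collected, with the IPD rules still open to change. Reported compliance may look less favourable. Because unreturned tablets count as taken, the two measures should be shown together and that limitation footnoted.

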9.2.7 Important Protocol Deviations

Important protocol deviations (IPD) are a subset of protocol deviations that may significantly impact the completeness, accuracy, or reliability of the study data or that may significantly affect a subject's rights, safety, or well-being. IPD rules will be developed and finalized before database lock.

The protocol deviations that should be considered as potential IPDs include, but are not limited to:

- Subject entered the study despite violation of any inclusion or exclusion criteria
- Subject was less than 80% compliant with study drug for non-safety reason

- Subject received prohibited concomitant medications
- Subject received the wrong treatment or incorrect doses
- Subject remained in the study despite meeting withdrawal criteria

Occurrence of any of these events should be considered as potential IPDs, but a blinded team should categorize them as IPDs only if they have the potential to significantly affect the completeness, accuracy, or reliability of the study data or that may significantly affect a subject's rights, safety, or well-being.

IPDs (from the clinical database or from the site deviation log) will be summarized descriptively based on the FAS and presented by treatment group and overall. Additionally, IPDs will be provided in an individual subject data listing.

9.3 Efficacy Analysis

There is no multiplicity adjustment in this study; *P*-values provided for the secondary and other endpoints are considered nominal.

All efficacy analyses described in this section will be based on the FAS, unless otherwise specified. The analysis will include all available measurements through the last scheduled on-treatment visit, including measurements after treatment discontinuation.

9.3.1 Analysis of the Primary Efficacy Variable

The primary efficacy endpoint is the absolute change in $LCI_{2.5}$ from baseline through Week 8. The objective of the primary efficacy endpoint analysis is to demonstrate that the mean absolute change from baseline in $LCI_{2.5}$ through Week 8 excludes a pre-defined maximum placebo effect in subjects in the TEZ/IVA group.

The primary analysis will be performed using a restricted maximum likelihood (REML)-based mixed-effect model for repeated measures (MMRM) for the subjects in the TEZ/IVA treatment group in the FAS population. The model will include absolute change from baseline in $LCI_{2.5}$ (including all measurements up to Week 8 [inclusive], both on treatment measurements and measurements after treatment discontinuation) as the dependent variable, and visit (as a class variable) as a fixed effect, with adjustment for mutation group based on the second *CFTR* allele (F/F and F/RF) and baseline $LCI_{2.5}$ (continuous) value as covariates, and subject as a random effect. An unconstructed covariance structure will be used to model the within-subject errors. If the model fails to converge, a compound symmetry covariance structure will be considered. The degrees of freedom of the denominator will be approximated by the Kenward-Roger's method².

The primary results obtained from the model will be the estimated average treatment effect through Week 8 in $LCI_{2.5}$ for subjects on TEZ/IVA. The corresponding LS mean, standard error (SE), 95% CI, and *p*-value will be provided. If the upper bound of the 95% CI is below the pre-defined maximum possible placebo effect, which was specified in the protocol, it will be considered that the study has achieved its primary objective. Summary statistics for change from baseline in $LCI_{2.5}$ through Week 8, and at each visit will also be provided for subjects in the TEZ/IVA treatment group by mutation groups and overall.

For F/F subjects in the placebo treatment group, summary statistics will be provided for change from baseline in LCI_{2.5} through Week 8, and at each visit.

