**Figure 2-1 VX16-661-115 Study Design**

**F/F Subjects**

**F/RF Subjects**

Notes: Subjects who are taking commercially available CFTR modulators (Orkambi® or Kalydeco®) are required to washout for 28 days before the Day 1 Visit. Study drug dose is determined based on weight on Day 1 (<40 kg or ≥40 kg). Subjects will receive matched TEZ/IVA placebo or IVA placebo tablets as appropriate. See [Table 9-2](#) for additional information on study drug tablets and dosing.

Subjects will be offered the opportunity to enroll in a 96-week open-label TEZ/IVA extension study (Study VX17-661-116) after completing the Week 8 Visit. The Safety Follow-up Visit is not required for subjects who enroll in the extension study within 4 weeks after the last dose of study drug.

Subjects who prematurely discontinue study drug treatment will be asked to remain in the study and complete the efficacy assessments (LCI, CFQ-R, sweat chloride, [REDACTED]) from the time of discontinuation through the end of the Treatment Period. Subjects who are discontinued due to having an ineligible genotype or due to lack of health authority approval will complete the ETT Visit and are not required to return for additional efficacy assessments because they will be discontinued from the study.

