**Table 9-1 Lifestyle Guidelines and Study Restrictions**

Restricted Medication/Food	Study Period	
	Screening Period	Treatment Period
Certain fruits and fruit juices (grapefruit, grapefruit juice, Seville oranges, marmalade)	None allowed within 14 days before the first dose of study drug	None allowed through the Safety Follow-up Visit
Moderate and strong CYP3A inducers	None allowed within 14 days before the first dose of study drug	None allowed through the Safety Follow-up Visit
Strong and moderate CYP3A inhibitors (except Ciprofloxacin)	None allowed within 14 days before the first dose of study drug	None allowed through the Safety Follow-up Visit
Investigational or physician-prescribed Orkambi (LUM/IVA) or Kalydeco	None allowed within 28 days before the Day 1 Visit	None allowed through the last dose of study drug
Commercially available TEZ/IVA	None allowed within 28 days before the first dose of study drug	None allowed through the last dose of study drug
Other investigational drugs or devices	None allowed within 30 days or 5 half-lives before screening, or time determined by local requirements; whichever is longer	None allowed through the Safety Follow-up Visit

Note: The use of restricted medication in subjects with a medical need will be addressed on a case-by-case basis with the medical monitor or authorized designee. See the Study Reference Manual for a more complete list of medications prohibited/restricted in the study.

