## 9.5 Prior and Concomitant Medications

Subjects will abstain from all restricted concomitant medications as described in the exclusion criteria ([Section 8.2](#)).

Information regarding all prior and concomitant medications, including the subject's CF medications, other medications, and herbal and naturopathic remedies administered from

4 weeks before the Screening Period through the Safety Follow-up Visit will be recorded in each subject's source documents and electronic case report form (eCRF).

- It is recommended that subjects remain on their stable medication regimen for CF from 4 weeks before Day 1 through Week 8 or, if applicable, through the Safety Follow-up Visit. Stable medication regimen is defined as the current medication regimen for CF (except for commercially available CFTR modulators) that subjects have been following for at least 4 weeks before Day 1. Subjects must not initiate long-term treatment with new medication from 28 days before Day 1 through the Safety Follow-up Visit unless discussed and approved by the Vertex medical monitor. Guidelines for stable medication regimens for CF are as follows:
  - Subjects who are taking daily inhaled tobramycin or other chronically inhaled antibiotics should remain on that regimen throughout the study.
  - Subjects who are on inhaled cycling antibiotics should continue on their prior schedule. The timing of the first dose of study drug should be synchronized as closely as possible to the first day of inhaled cycling antibiotics in the cycle.
  - Subjects who alternate 2 different antibiotics monthly should remain on the same schedule during the study. The timing of the first dose of study drug should be synchronized as closely as possible to the first day of 1 of the inhaled alternating antibiotics.
- Subjects may receive doses of prednisone (or prednisolone) of up to 10 mg/day (chronically), or prednisone (or prednisolone) 60 mg qd for up to 5 days with tapering down to 10 mg/day within 2 weeks, without prior approval of the medical monitor.
- Information about bronchodilator use during the study will be collected and documented. Subjects who are using a bronchodilator must have their spirometry assessments performed according to the guidelines provided in [Section 11.4.2](#).

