9.3.2 Analysis of Secondary Efficacy Variables

Absolute change in sweat chloride from baseline at Week 8

A similar MMRM model will be used for the above variable using the same approach as described for the analysis of the primary efficacy variable, with the addition of baseline sweat chloride as a covariate. The assessment of efficacy will be primarily based on the estimated mean change from baseline at Week 8.

Similar summary tables will also be provided using the same approach as described for the analysis of the primary efficacy variable.

Absolute change in the CFQ-R respiratory domain score from baseline through Week 8

A similar MMRM model will be used for the CFQ-R respiratory domain score based on the children's version, using the same approach as described for the analysis of the primary efficacy variable, with the addition of baseline CFQ-R respiratory score as a covariate.

Summary tables will also be provided for both the children's version and the parents/caregivers' version using the same approach as described for the analysis of the primary efficacy variable.

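### LCI measured after a child stops TEZ/IVA and starts another CFTR modulator would count toward TEZ/IVA success; the SAP has no rule for it, and the protocol is unclear on when it may occur

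*SAP*

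**What the plan says.** **Restriction on modulators.** In Protocol Table 9-1, the treatment-period entry for Orkambi/Kalydeco and for commercial TEZ/IVA is "None allowed through the last dose of study drug". Every other row (the listed fruits, CYP3A inducers and inhibitors, other investigational products) reads "None allowed through the Safety Follow-up Visit".

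**Limit on new medication.** Protocol 9.5 states: "Subjects must not initiate long-term treatment with new medication from 28 days before Day 1 through the Safety Follow-up Visit unless discussed and approved"; the approval meant is that of the medical monitor. The same section defines the stable CF regimen as the current regimen "except for commercially available CFTR modulators".

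**Follow-up after stopping.** The Protocol Synopsis (notes under Figure 2-1) states: "Subjects who prematurely discontinue study drug treatment will be asked to remain in the study and complete the efficacy assessments", naming LCI, CFQ-R and sweat chloride, to the end of the Treatment Period. Section 9.1.4 agrees.

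**Primary analysis.** SAP 9.3.1 fits a repeated-measures model to TEZ/IVA subjects only, "including all measurements up to Week 8 [inclusive], both on treatment measurements and measurements after treatment discontinuation". The objective is met if the upper 95% confidence bound is below the maximum placebo effect, set at -0.10 in SAP 7.2. SAP 9.3.2 analyses sweat chloride and CFQ-R "using the same approach as described for the analysis of the primary efficacy variable".

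**Other medication.** SAP 9.2.7 lists prohibited medication as a potential important protocol deviation, to be summarised and listed. No readable SAP text says how efficacy values collected after a non-study modulator starts are to be handled.

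**The concern.** The -0.10 threshold comes from placebo subjects in Study 809-109, and SAP 7.2 supports it by arguing that LCI worsens without a modulator. A value obtained on another modulator does not belong on the TEZ/IVA side of that comparison. In a trial with a control-arm contrast, later therapy could occur in both arms. Here nothing offsets it, and its direction favours success.

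The scenario is foreseeable. The protocol expects some children to arrive on prescribed Orkambi or Kalydeco and to wash out for 28 days before Day 1. If such a child stops study drug and goes back to the earlier modulator, later LCI values are read against a washed-out baseline, and the full benefit of that modulator is recorded as TEZ/IVA change.

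The secondary endpoints inherit the problem. For sweat chloride, the Week 8 window in SAP Appendix A runs to Day 71 and takes in a Safety Follow-up value that falls inside it. A value obtained after a switch can therefore stand as Week 8 if no scheduled value exists. The descriptive F/F placebo summary (about 10 children) could be blurred in the same way.

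**Working it through.** **1. Timing.** Safety Follow-up is 4 weeks (28 days, ±7) after the last dose, and Week 8 is targeted at Day 57.
- Stop on Day 14: Safety Follow-up is near Day 14 + 28 = Day 42, which is 15 days before Week 8.
- Stop at Week 3 (Day 21): near Day 49. A modulator in use at Week 4 falls inside the period limited by Protocol 9.5; one started between Day 49 and Week 8 falls outside it.
- In general, a last dose before about Day 57 - 28 = Day 29 puts Safety Follow-up before Week 8.

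**2. Where affected LCI can arise.** Table 3-1 schedules multiple-breath washout at Weeks 2, 4 and 8, but not at the Early Termination or Safety Follow-up visits. Affected values therefore come from those three visits or from unscheduled tests.

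**3. The plan's own power figure.** SAP 7.2 gives a true mean of -0.9, threshold -0.10, SD 1.41, two-sided alpha 0.05, about 40 subjects and 10% dropout. The difference is 0.8 and evaluable n = 40 × 0.9 = 36.
- SE = 1.41/√36 = 0.235, and 0.8/0.235 = 3.404.
- Normal approximation: Φ(3.404 - 1.96) = 92.6%. Noncentral t: 91.1%.

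The stated power of at least 90% is reproduced.

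**4. Effect of unhandled switching.** Inputs from the documents: SD 1.41; 52 TEZ/IVA subjects (40 F/F + 12 F/RF, Protocol Table 12-1); three post-baseline visits, weighted equally here. Assumptions: the other modulator gives an LCI change of -0.9 (borrowed from the SAP's planning value for TEZ/IVA), and the true TEZ/IVA mean is exactly -0.10. Each affected value then moves by -0.9 - (-0.10) = -0.8.

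SE = 1.41/√52 = 0.1955

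Shift = (k/52) × (share of visits) × (-0.8)

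One-sided error = Φ(-1.96 + |shift|/SE)

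| Children (k) | Visits affected | Shift | \|Shift\|/SE | One-sided error |
|---|---|---|---|---|
| 0 | – | 0 | 0 | 2.5% |
| 1 | 2 of 3 | -0.010 | 0.052 | 2.8% |
| 2 | 2 of 3 | -0.021 | 0.105 | 3.2% |
| 5 | 2 of 3 | -0.051 | 0.262 | 4.5% |
| 5 | 3 of 3 | -0.077 | 0.393 | 5.9% |

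Five children is about 10% of 52 (5.2).

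**5. Sensitivity to the assumed effect.** If the gap between the two effects were half as large (0.4 instead of 0.8), the last three rows become -0.010 and 2.8%, -0.026 and 3.4%, and -0.038 and 3.9%.

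**6. At the planning effect.** If the true TEZ/IVA mean is -0.9, each affected value moves by -0.9 - (-0.9) = 0, and the mean is not shifted.

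**The case against.** **The protocol does not simply allow modulators after the last dose.** A reader of Table 9-1 alone might infer that it does. Protocol 9.5 requires medical monitor approval for new long-term medication up to Safety Follow-up, and because modulators are left out of the stable regimen, a restart can fairly be read as new. This stands, so the documents support an ambiguity and not an open permission. It does not close the gap: the limit can be waived, its reach over a washed-out drug is unstated, and it can end before Week 8.

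**Including post-discontinuation data is deliberate and consistent across both documents.** This also stands. Off-drug values without another modulator would tend to dilute the effect, so a reader should not infer that including them is itself anti-conservative. The treatment-policy argument is weak only for values on another modulator, because no concurrent arm is compared.

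**The numbers rest on severe inputs.** The 10% is a sample-size allowance. The last table row needs all five children to stop, switch and supply LCI on the new drug from Week 2 onward. Giving -0.9 to the other modulator while TEZ/IVA sits at the threshold is also hard to square with one of those modulators being commercial TEZ/IVA. All of this stands, which makes that row an upper bound.

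**Setting values to missing is not neutral.** Under missing at random, the model predicts early stoppers from children who stayed in the TEZ/IVA arm, which can also favour success. This stands and shapes the fix.

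**Conclusion.** The point holds as a conditional weakness of modest size. Table 9-1 and Protocol 9.5 do not settle when a child who has stopped study drug may be on another modulator, and they must be reconciled. Which clinical rule is right is not a matter for this review. Whichever rule is kept, SAP 9.3.1 would count any LCI obtained on another modulator toward TEZ/IVA success.

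Under the stated assumptions, one-sided error rises from 2.5% to about 3.2% with two children affected at two visits, to 4.5% with five, and to 5.9% at the upper bound. A reader might charge each affected value with the full -0.9, which gives larger figures. At a true mean of -0.10 those values would already average -0.10, so only 0.8 is gained. Nor do the documents support concluding that a clear success would be false: at the planning effect the shift is about zero. The point matters mainly for a borderline result, and redacted text could hold related analyses that cannot be seen. It should be fixed before unblinding, but it does not undermine the design.

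**What to change.** 1. In SAP 9.3.1 and 9.3.2, set LCI, sweat chloride and CFQ-R values collected after the first dose of any non-study CFTR modulator to missing in the main analysis. Apply the same rule to the F/F placebo summaries. Keep all other post-discontinuation values, as now.
2. Record modulator start dates through each child's last efficacy visit. Table 3-1 and Protocol 9.5 stop recording medication at Safety Follow-up, which for an early stopper can precede Week 8.
3. Report how many children, and how many values, are affected in each arm.
4. Run two sensitivity analyses: the current all-measurements analysis, and one that gives the removed values an unfavourable change, for example no change from baseline. The second guards against the favourable pull of missing at random in a one-arm test. SAP 9.1 rules out imputation unless otherwise specified, so this exception must be written in.
5. Reconcile Table 9-1 with Protocol 9.5.

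The cost is a few sentences in the SAP, which is to be finalised before database lock and unblinding, plus a small amount of extra recording. A few late values are lost from the main analysis, and a child who switched before Week 2 would contribute no post-baseline LCI to it.
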